Different models have been used to study glucagon regulation ^(13,14,15,16). Since both hyperglycemia and hypoglycemia stimulate alpha cells to produce glucagon, both the lack of intra-islet insulin and this U-shaped glucagon response contribute to glucose dysregulation in T1D ^(17,18). It has been reported that in T1D patients with a duration of the disease of 26.4±7.5 years, glucagon levels increased in response to the OGTT under euglycemic and hyperglycemic conditions ⁽¹⁹⁾, however the relative contribution of hyperglucagonemia to post-prandial glucose rise in the presence or absence of pre-prandial insulin has not been clearly elucidated. Whether appropriately timed exogenous insulin can modify the glucagon response to glucose fluctuations has not been studied.

Research Objective:

To characterize the glucagon response to meal-time hyperglycemia and to compare the difference in glucagon secretion when mealtime bolus insulin is given before the meal versus after the meal with the objective of understanding factors that contribute to the peak post-prandial blood glucose and AUC of blood glucose after a mixed meal in this target population.

Research Hypothesis:

1. Patients with higher glucagon responses to a mixed meal stimulus will have higher peak post-prandial glucoses and greater AUC of post-prandial glucose.
2. Bolus dose insulin given pre-meal (20 min before meal) will result in lower peak post-prandial glucose, lower AUC and lower post-prandial glucagon levels
3. Bolus dose insulin given post-meal (20 min after meal) will result in higher peak post-prandial glucoses, higher AUC of post-meal glucose and higher glucagon levels
4. There will be a correlation between peak post-prandial glucagon response and post-meal glucose AUC, 0 to 180 minutes

Potential Contribution:

Glucagon regulation and response in persons with T1D at the basal state and in response to various stimuli remains unclear. An important gap in our knowledge is whether the timing of prandial insulin doses affects the glucagon response to a hyperglycemic stimulus in patients with T1D who have undetectable C-peptide. Understanding the mechanisms behind the higher post-prandial peak in glucose with delayed insulin administration may help clinicians guide appropriate timing of insulin administration for T1D patients with long course of the disease

METHODS

Recruitment:

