Alpha cell function will be assessed by measuring fasting and post-prandial glucagon and calculation Area under the Curve ratio (AUC-Glucagon 0-180min/AUC-Glucose 0-180min). Some of the participants characteristics will include in the study are: Demographics, BMI, history of DKA, DKA at onset of diagnosis, diabetes comorbidities (Retinopathy, cardiovascular, nephropathy, neuropathy), concomitant autoimmune disease, type and dose of insulin,

Methods of Data Analysis

Data analysis will be performed using STATA 15.1 for Windows (StataCorp LP, College Station, Texas, United States). The sample size calculation assumes that the peak postprandial glucose will increase by 80 +/-20 mg/dl in the pre-meal insulin group and 140 +/-20 mg/dl in the post-meal group. So, the expected mean peak of postprandial glucose will be up to 220 mg/dL for Visit A and mean peak postprandial glucose will be up to 280 mg/dL for Visit B. The sample size will have 80% power to detect a difference between groups at $p < 0.05$. We have assumed correlation between visits A and B of 0.5. The sample size was corrected by an anticipated loss of follow up of 10% of the participants. The calculated sample size is 10 participants with full

data sets available for 8 participants. The study randomization is designed as follows: 5 participants will first attend Visit A, and then Visit B. The 5 remaining participants will first attend Visit B and then Visit A. AUC of post-prandial glucose and glucagon and maximum postprandial peak of glucose and glucagon will be analyzed by using paired T student. Relationships between variables were assessed by a Spearman's correlation test.

REFERENCES

1. Cryer PE. Minireview: Glucagon in the pathogenesis of hypoglycemia and hyperglycemia in diabetes. *Endocrinology*. 2012;153(3):1039-1048. doi:10.1210/en.2011-1499
4. Yosten GLC. Alpha cell dysfunction in type 1 diabetes. *Peptides*. 2018;100:54-60. doi:10.1016/j.peptides.2017.12.001

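### Four outcomes are tested with no primary and no multiplicity rule, and the 80% power statement rests on peak glucose alone, so glucagon, which leads the objective, has no power basis

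*Combined protocol and SAP*

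**What the plan says.** All references are to the combined protocol and SAP.

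- **Methods of Data Analysis, tests.** "AUC of post-prandial glucose and glucagon and maximum postprandial peak of glucose and glucagon will be analyzed by using paired T student". Relationships between variables go to Spearman correlations. No outcome is labelled primary, and no rule says how several p-values are to be combined.
- **Methods of Data Analysis, sample size.** The inputs are that "peak postprandial glucose will increase by 80 +/-20 mg/dl in the pre-meal insulin group and 140 +/-20 mg/dl in the post-meal group", and "We have assumed correlation between visits A and B of 0.5". Then: "The sample size will have 80% power to detect a difference between groups", at p < 0.05. That is the only significance level in the document, and sidedness is not stated. The result is 10 participants, with full data for 8.
- **Research Objective.** The aim opens with the glucagon response to the meal and is "to compare the difference in glucagon secretion when mealtime bolus insulin is given before the meal versus after the meal". It continues by naming peak post-prandial glucose and glucose AUC as the quantities to be understood.
- **Research Hypothesis.** Pre-meal insulin "will result in lower peak post-prandial glucose, lower AUC and lower post-prandial glucagon levels"; the post-meal hypothesis mirrors this. Two further hypotheses relate glucagon to post-prandial glucose.

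No glucagon effect size, SD or power appears anywhere.

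**The concern.** Two gaps meet here. First, with four tests and no designated primary, the result that counts can be chosen after the data are seen, and the error rate attached to that choice is not 5%. Second, the only power statement is worded generally, as a difference between groups, while its inputs are for peak glucose alone. The effect of insulin timing on glucagon is what the protocol presents as the gap in knowledge, and the document gives no indication of what size of glucagon effect about 8 pairs can detect.

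The practical risk is a paper reporting a clear glucose difference and a non-significant glucagon difference, with the second read as evidence that timing does not affect glucagon. Conversely, one glucagon p-value just under 0.05, out of two, could be presented as a finding with a 5% error rate.

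**Working it through.** **1. The plan's own sample size.** Inputs from Methods of Data Analysis: rises of 80 and 140 mg/dL (difference 60), ±20 read as the SD at each visit, correlation 0.5, 10% loss. Two-sided 0.05 is assumed.

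SD of the paired difference = √(20² + 20² − 2 × 0.5 × 20 × 20) = √400 = 20. Standardised paired difference = 60/20 = 3.0.

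Exact (noncentral t) power for a paired t-test at 3.0:

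| Pairs | Power |
|---|---|
| 3 | 74.5% |
| 4 | 96.7% |
| 8 | above 99.9% |

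The paired test therefore needs 4 completers, and 4/0.9 = 4.4 rounds up to 5 enrolled. The stated 8 and 10 are not reproduced. They do match an unpaired two-sample t-test: 3 per group give 78.3% and 4 per group 93.9%, so 4 per group (8 in total), and 4/0.9 rounds up to 5 per group (10 in total). That calculation uses neither the stated correlation nor the paired analysis. The documents do not say how 10 was obtained, so this is a match and not a demonstrated cause.

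**2. Chance of at least one p < 0.05 when no outcome truly differs.** Assume each of the four tests is run at 0.05.

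Independent tests: 1 − 0.95⁴ = 18.5%.

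Peak and AUC of one analyte come from the same five samples, so they will be correlated. The documents give no correlation between outcomes; the values below are assumed. Simulation, 100,000 runs, 8 pairs:

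| Peak–AUC correlation, same analyte | Glucose–glucagon correlation | Any of four | Either glucagon test |
|---|---|---|---|
| 0.7 | 0.3 | 16% | 9% |
| 0.8 | 0.5 | 15% | 8% |
| 0.9 | 0.5 | 13% | 7% |
| 0.95 | 0.7 | 11% | 7% |

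**3. The same, if the glucose effect is real.** Only the two glucagon tests can then be false positives. Independent: 1 − 0.95² = 9.75%. Correlated: the last column, 7–9%.

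**4. What 8 pairs can detect for glucagon.** Solving noncentral t power = 80% with 7 degrees of freedom at two-sided 0.05 gives a mean paired difference of 1.16 SD of the differences; with 10 pairs it is 1.00 SD. Power at assumed true effects:

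| True effect (SD of differences) | 8 pairs | 10 pairs |
|---|---|---|
| 0.5 | 23% | 29% |
| 0.8 | 50% | 62% |
| 1.0 | 68% | 80% |
| 1.2 | 83% | 92% |

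**5. Cost of a Bonferroni split instead.** At 0.05/4 = 0.0125 per test, the detectable difference with 8 pairs rises from 1.16 to 1.53 SD.

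**The case against.** The strongest reply is that peak glucose is already the primary outcome in all but name: the sample size is built on it, and the power sentence directly follows the peak-glucose assumptions, so in context it makes no promise about glucagon. The objective also names peak glucose and glucose AUC. And the two insulin-timing hypotheses are worded as conjunctions; if a hypothesis were claimed only when every part is significant, there would be no inflation. For a 10-person mechanistic crossover, this is then mostly labelling.

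Much of this stands, and it rules out stronger readings that a reader might infer:

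- *That the false-claim rate is simply 13–18%.* That needs all four nulls to be true, contrary to the plan's own 60 mg/dL assumption; the upper end also needs near-independence of measures taken from the same samples.
- *That the plan sets each test at 0.05, with any one sufficing for a claim.* The level appears only in the sample-size sentence. Its use for each test is an inference, and the plan states no decision rule at all.
- *That the objective is glucagon alone, or that the plan claims 80% power for glucagon.* Neither is written.
- *That the trial is too large.* High power for peak glucose does not make 8 pairs sufficient for glucagon.

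What does not stand is the idea that context makes the fix unnecessary. An implied primary is not a pre-specified one, particularly when the objective opens with a different analyte. Nor does the conjunctive wording amount to a decision rule.

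**Conclusion.** The point holds in a limited form. Four paired tests have no designated primary and no multiplicity rule in the available text. (Part of the document was removed before review, so a label there cannot be excluded.) The error rate depends on what is true: 18.5% under independence, or about 11–16% under the assumed correlations, if nothing differs; about 7–10% for a false glucagon claim if the glucose effect is real. The second scenario is the one the plan itself expects. Both assume that every test is run at two-sided 0.05 and that any significant result may be claimed.

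The power figure applies to peak glucose only, and even there it does not reproduce: above 99.9% with 8 pairs, not 80%, with ±20 read as an SD. For glucagon, a non-significant result would say little unless the true effect is near or above 1.16 SD of the differences. Whether that is large in glucagon units cannot be judged, because no glucagon SD is given. This should be corrected, but it does not invalidate the design.

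**What to change.** In Methods of Data Analysis:

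1. Name peak post-prandial glucose, already the sample-size endpoint, as the single primary, tested at 0.05 with sidedness stated.
2. Label glucose AUC, glucagon AUC and peak glucagon as secondary, and the Spearman correlations as exploratory.
3. Restate the power sentence as applying to peak glucose only, with the recomputed value for the paired test. Add that 8 pairs give 80% power for glucagon only at about 1.16 SD of the paired differences.
4. Report 95% confidence intervals for all four paired differences, and state that a non-significant glucagon result will not be read as absence of effect.
5. If a formal glucagon claim is wanted, pre-specify one glucagon endpoint, tested at 0.05 only if peak glucose is significant. This keeps the error over the two tests at 5% without the Bonferroni penalty. It should not have to pass through glucose AUC first, because the plan gives no assumptions for that outcome. On the plan's inputs the peak-glucose step almost never fails.

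The cost is wording only: no added participants, visits or assays. The downside is that the remaining outcomes support only descriptive statements. The choice between glucagon AUC and peak glucagon is the investigators' to make, before the data are seen.

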16. Liu Y-J, Vieira E, Gylfe E. A store-operated mechanism determines the activity of the electrically excitable glucagon-secreting pancreatic alpha-cell. *Cell Calcium*. 2004;35(4):357-365. doi:10.1016/j.ceca.2003.10.002

Date:

Patient Name:

DOB:

MRN:

Evaluator:

Visit A:

BP: HR: RR: T: Weight: BMI:

1. Demographic information:

- a. Age
- b. Sex:
- c. Married:
- d. Time of the disease (T1D)
- e. History of DKA
- f. DKA at onset of diagnosis
- g. Diabetes comorbidities (Retinopathy, cardiovascular, nephropathy, neuropathy)
- h. Concomitant autoimmune disease
- i. History of hypoglycemia,
- j. Hypoglycemia unawareness

2. T1D:

- Diabetes medications:
 - a. Oral:
 - b. Non-injectable insulin
 - c. Insulin
- ICR
- Statins:

3. Allergies:

4. Meal time prandial insulin dose to be used (in second visit)
5. Physical Examination:
 - a. General:
 - b. HEENT:
 - c. Cardio:
 - d. Lungs:
 - e. GI:
 - f. Extremities:
 - g. Skin:
 - h. Neuro:
6. Labs:
 - Fasting C-peptide
 - CBC (if required)
 - GFR (if required)
 - A1C (if required)
7. Glucose Target prior intervention: (Baseline glucose should be 80 to 140 mg/dl. In case baseline glucose is not in the target range, the study visit will be rescheduled): Yes, No
8. Intervention:

Usual insulin dose will be administered 20 minutes **prior** to a mixed meal challenge with Ensure Plus

 - Glucose levels:
 - Fasting:
 - 30 min:
 - 60 min:
 - 120 mins:
 - 180 min:
 - Glucagon levels:
 - Fasting:
 - 30 min:
 - 60 min:
 - 120 mins:
 - 180 min:
9. Was the intervention hold? Yes, No Reason:

Visit B:

BP: HR: RR: T: Weight: BMI:

1. Glucose Target prior intervention: (Baseline glucose should be 80 to 140 mg/dl. In case baseline glucose is not in the target range, the study visit will be rescheduled): Yes, No
2. Physical Examination:
 - a. General:
 - b. HEENT:
 - c. Cardio:
 - d. Lungs:
 - e. GI:
 - f. Extremities:
 - g. Skin:
 - h. Neuro:

3. Intervention

Usual insulin dose will be administered 20 minutes **post** to a mixed meal challenge with Ensure Plus

- Glucose levels:
 - Fasting:
 - 30 min:
 - 60 min:
 - 120 mins:
 - 180 min:
- Glucagon levels:
 - Fasting:
 - 30 min:
 - 60 min:
 - 120 mins:
 - 180 min:

4. Was the intervention hold? Yes, No Reason:
